Memory and Attention Adaptation Training-Geriatrics (MAAT-G) is a cognitive behavioral therapy-based intervention for targeting modifiable factors of CRCD for older adults.²⁰⁻²³ MAAT-G provides instruction and practice with adaptive behavioral coping skills, stress management techniques, and compensation strategies for episodes of cognitive failure (e.g. lapses in memory, attention). MAAT-G is derived from an existing CRCD intervention (MAAT), and was adapted for the unique needs of older adults. MAAT-G is a series of ten manualized workshops delivered by a trained clinician (e.g. psychologist, psychology post-doctoral fellow, psychology intern or Research Nurse) via video-conferencing combined with a participant workbook. In younger cancer survivors (i.e. those who have completed chemotherapy), the original MAAT intervention was shown to improve self-perceived cognition (Functional Assessment of Cancer Therapy—Cognition [FACT-Cog], $d=0.52$), verbal memory (California Verbal Learning Test 2 (CVLT), $d=-0.63$) and processing speed (Symbol Digit Subtest of Telephone Based Neuropsychological Status [TBANS], $d=0.5$).^{11,26} These cognitive functions are particularly important for older adults; and we propose to deliver MAAT-G alongside systemic cancer therapy to mitigate the development of CRCD (when risk is highest) and CRCD-related effects on functional independence for older adults.

Study Objective:

Primary Objective:

- Examine the preliminary effect of MAAT-G on FACT-Cog.
 - Hypothesis: Patients receiving MAAT-G will have better perceived cognition (FACT-Cog) compared to control at follow-up.

Secondary Objectives:

- Estimate MAAT-G's effect on function (e.g. IADL) and objective neuropsychological measures including CANTAB, FACT-Cog, COWA, HVLT-R, GDS, Brief Test of Adult Cognition by Telephone (BTACT), and GAD-7.
 - Hypothesis: Patients receiving MAAT-G will have better short-term visual/spatial memory, sustained attention, visual memory/new learning, verbal fluency, verbal learning and memory, and function compared to control at follow-up.
- Develop a more complete understanding of the patient and caregiver experience with MAAT-G and their perceptions of MAAT-G's benefits on cognition and function beyond what is captured by quantitative measures alone, through integration of quantitative

data with semi-structured interviews.

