6.0 REGISTRATION AND RANDOMIZATION

6.1. Registration:

To register a participant who meets the eligibility criteria and who has signed the informed consent document, study staff will enter the information outlined in section 6.2 in the OnCore database.

6.2. Information Requested at Registration:

- 6.2.1** Firstname
- 6.2.2** Last name
- 6.2.3** eMRN
- 6.2.4** Birth Date
- 6.2.5** Gender
- 6.2.6** Race
- 6.2.7.** Ethnicity

6.3. Initial Assessment:

After consent procedures are completed, the patient, with the help of the study coordinator, will complete a baseline assessment (See section 7).

6.4 Randomization Procedures:

The two intervention arms are as follows:

Arm 1= MAAT-G intervention

Arm 2 = Supportive therapy (time and attention control)

A computer-generated random numbers table, stratified by stage (local [stage I-III] and advanced [stage IV]) with equal probability of block size 2 or 4 will be used to assign participants to one of the two treatment arms. The randomization will assign participants to the two arms in the ratio 1:1. The random numbers tables will be generated centrally using R software. A total enrollment of 85 participants is planned to accommodate for potential 15% attrition, with at least 35 participants in each treatment arm.

Subjects can be registered prior to obtaining baseline measures however, subjects will not be aware of which arm they are randomized to until after the baseline assessment. After registered, they will be scheduled to undergo baseline measures. At the end of the visit for baseline assessment, they will be randomized.

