Functional Independence: IADLs will be measured⁵⁹. IADL will be administered by the study coordinator over the phone or via televideo (Zoom application) at the appropriate time points.

Phase II semi-structured interview questions for patients and caregivers will focus on perceptions of cognitive change and potential benefit of intervention sessions.

7.1 Study Procedures:

Baseline: Following informed consent, patients will undergo Time Point (TP) 1 assessment. Patients will be provided with a data-enabled tablet with HIPAA-compliant video-conferencing application and instructed on its use, participant workbook (for MAAT-G intervention participants only), and tablet instruction manual. The study coordinator will give the patients a drawstring bag to hold all study materials given at TP1. At the time of enrollment, the study coordinator will assign each patient a unique meeting ID number within the tablet instruction manual. This meeting ID number allows each patient to log on to the video-conferencing application and speak to trained clinician (e.g. the MAAT-G Interventionist). Study coordinators will train and support patients on the use of the tablet and video conferencing application. No data is being stored on the tablet itself. If patients consent to have sessions recorded, this will be done through the HIPAA-compliant Zoom software application. If participants do not have access to wireless internet, the tablet will be equipped with a data package for participant use for the purposes of this study. At completion of the study, patients will return the tablet to the study coordinator. If the tablet is lost or stolen during the study, no PHI will be stored on the tablet and thus would not be accessible. If the tablet is broken during the course of the study, we will provide participants with another tablet for use during the study period. The participant would contact the study coordinator with any concerns or problems with using the tablet, contact information will be provided during training on tablet use.

Intervention Period: The intervention period is 10-12 weeks; 10 weekly workshops will be delivered through video-conferencing on the tablet. Workshops will be audio-recorded for fidelity review. (See section 7.2)

Follow-up: Within 1 day to 4 weeks of intervention completion (approximately week 10-14), patients will undergo TP2 assessment.

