Supportive Therapy (ST) is a “behavioral placebo” and controls for non-specific psychotherapeutic factors of the clinician-subject relationship, such as empathy and support, but does not provide active cognitive training. ST utilizes reflective listening to help deepen awareness of participants’ emotional experience. ST was used as the control condition for a prior MAAT study.⁷¹ A clinician manual for ST has been developed.⁷¹ Timing and duration of ST sessions will mirror the intervention, and will consist of 10 weekly sessions, 30 to 45 minutes each, delivered by a trained clinician (e.g. psychologist, psychology post-doctoral fellow, psychology intern, or Research RN) via video-conferencing.

We will offer subjects who are randomized to the Supportive Therapy (ST) group the opportunity to receive the MAAT-G Intervention after their completion of the 10 ST sessions and the post-intervention follow-up time point procedures. We will not administer an additional evaluation during this time period if patients elect to proceed with MAAT-G after completing study procedures (e.g. no further time points for followup of cognition or survey measures). If patients do elect to continue with this, we will continue to monitor for potential adverse events that are related to the behavioral intervention (see Data Safety Monitoring section below). Participants electing to continue and receive MAAT-G after completing study procedures can discontinue at any time. If subjects decide to get the MAAT-G intervention, they do not need to complete all 10 sessions or within a certain timeframe. We will collect data on the number of ST subjects who chose to do the additional MAAT-G Intervention and the number of sessions completed. The intent of allowing patients randomized to ST to continue and receive MAAT-G after completion of study procedures is to facilitate retention.

The University Advarra system will be used per WCI policy for study reimbursement for \$30 per time point/workshop. The templated RSRB information for Advarra will be used for information for patients for use of the gift card system. The study team will collect W-9 to sent to University Accounts Processing for study payment documentation and send to [contact]. Following this, the participant W-9 will be shredded. W-9 information will not be kept by the study team.

7.3. Potential risks:

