Quantitative Data Analysis: Underlying assumptions to all statistical analyses will be checked using appropriate graphical and numerical methods.⁷² In the case of serious violation of assumptions, appropriate transformations or nonparametric methods will be used.^{73,74} If outlying observations are encountered, data will be checked. If no errors are found, we will conduct analyses with and without the outlying data and compare results. Bivariate associations between treatment group and participant variables (demographics, cancer and treatment characteristics, baseline assessment of outcome measures) will be examined to assess possible imbalance between arms. Since this is a pilot study, will use significance level=0.10 to avoid false negative results, and decrease the risk of abandoning a promising intervention.^{75,76}

Analysis of the primary outcome: To assess the impact of the intervention on patient-reported cognition (FACT-Cog), we will employ the analysis of covariance (ANCOVA). The model will consist of post-FACT-Cog as the outcome and include the arm as the main effect and pre-FACT-Cog as a covariate. We will evaluate the interaction between pre-FACT-cog and the arm. We will adjust for baseline covariates in case that imbalance between arms was detected, and baseline and change in psychological measure (GDS and GAD-7). All non-significant covariates will be removed from the model.

Analysis of secondary and exploratory outcomes: The effect of MAAT-G on objective cognition (CVLT-R, TBANS, CANTAB, COWA, HVLT-R, TMT A/B), functional independence (IADL) and stress response (cortisol) will be assessed with the same strategy as for the primary outcome.

As above, a sample size of 85 patients is planned based upon anticipated attrition rates. If attrition of patients occurs at a higher proportion than anticipated during the trial conduct, we will conduct an interim data analysis check to assess for need in adjusting sample size.

Phase II Qualitative Data Analysis: Semi-structured interviews will be prepared and coded similar to Phase Ib. Potential themes from Phase II interviews include experiences of cognitive failure and perceived timing and mode of onset of symptoms, changes in functional independence, perception of how the intervention (either MAAT-G or ST) influenced symptoms and experience, and experiences with the adaptive behavioral or compensatory techniques used.

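### The primary ANCOVA adjusts for change in GDS and GAD-7, which is measured after randomisation, so the arm coefficient need not estimate MAAT-G's total effect on FACT-Cog

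*Combined protocol and SAP*

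**What the plan says.** The primary hypothesis in section 2.0 is: "Patients receiving MAAT-G will have better perceived cognition (FACT-Cog) compared to control at follow-up". For the primary outcome, section 8.2 specifies an ANCOVA of post-FACT-Cog on arm with pre-FACT-Cog as covariate. It continues: "We will adjust for baseline covariates in case that imbalance between arms was detected, and baseline and change in psychological measure (GDS and GAD-7". The next sentence gives the retention rule: "All non-significant covariates will be removed from the model".

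The timing is clear. Section 6.4 says of participants: "At the end of the visit for baseline assessment, they will be randomized". Section 7.1 (Follow-up) says: "Within 1 day to 4 weeks of intervention completion (approximately week 10-14), patients will undergo TP2 assessment". The secondary objectives in section 2.0 put both scales among the measures on which MAAT-G's effect is to be estimated: "objective neuropsychological measures including CANTAB, FACT-Cog, COWA, HVLT-R, GDS, Brief Test of Adult Cognition by Telephone (BTACT), and GAD-7".

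Section 8.2 carries the approach to the secondary and exploratory outcomes, namely objective cognition, IADL and "stress response (cortisol) will be assessed with the same strategy as for the primary outcome". BTACT, GDS and GAD-7 are not in that list.

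**The concern.** A change score in GDS or GAD-7 is known only after the intervention, so it is a possible consequence of the assigned arm. Conditioning on it removes from the arm coefficient whatever part of the FACT-Cog difference goes with mood. The hypothesis makes no such subtraction: it compares FACT-Cog between arms at follow-up. Nowhere do the documents name a direct-effect or mediation estimand, or say that the fit without the change terms is the one to be reported.

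An arm difference in mood is possible in either direction. MAAT-G is CBT-based and includes relaxation, cognitive restructuring, activity pacing and sleep (section 7.2a, Table 2). Supportive therapy works directly on emotional experience (section 7.2b). The primary estimate could therefore be too low or too high. Section 8.2 chooses a 0.10 level so as not to abandon a promising intervention; if MAAT-G helps mood more, this adjustment raises that very risk.

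**Working it through.** **Inputs from section 8.2.** 35 evaluable per arm; standardised effect d = 0.52; pre-post correlation r = 0.5; significance level 0.10, taken as two-sided in line with section 8.1.2.

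**Inputs assumed, because the documents give none.** ρ = correlation of mood improvement with post-FACT-Cog within arm, given baseline: 0.3 to 0.5. a = between-arm difference in mood improvement in SD, positive when it favours MAAT-G: −0.5 to 0.5. GDS and GAD-7 change are treated as one combined term.

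**Step 1: the plan's own figure.** For arm plus pre-FACT-Cog, SE = √(1 − r²) × √(2/35) = 0.866 × 0.239 = 0.207. Then 0.52/0.207 = 2.51, and the noncentral t with 67 df gives 80.0% power. The stated sample size is reproduced and is not in question.

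**Step 2: add the mood-change term.**

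- Adjusted effect = 0.52 − ρ × √(1 − r²) × a
- SE = √(1 − r²) × √(1 − ρ²) × √(2/35) × √(1 + a²/4)
- Power from the noncentral t with 66 df

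Mildest case of a moderate difference, ρ = 0.3 and a = 0.3: effect = 0.52 − 0.3 × 0.866 × 0.3 = 0.442; SE = 0.200; power 71%.

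Extreme case, ρ = 0.5 and a = 0.5: effect = 0.52 − 0.5 × 0.866 × 0.5 = 0.303; SE = 0.185; power 49%.

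| Mood difference | Estimate (true 0.52) | Power |
|---|---|---|
| 0 | 0.52 | 83–89% |
| 0.1–0.2 SD favouring MAAT-G | 0.43–0.49 | 76–84% |
| 0.3–0.5 SD favouring MAAT-G | 0.30–0.44 | 49–71% |
| 0.3–0.5 SD favouring supportive therapy | 0.60–0.74 | – |

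**Step 3: where the gain turns into a loss.** At ρ = 0.3, power is 83.2% at a = 0 and 79.6% at a = 0.1; interpolating, it reaches 80% at 0.1 × 3.2/3.6 = 0.09 SD. At ρ = 0.5, it is 83.7% at a = 0.1 and 76.9% at a = 0.2, so it reaches 80% at 0.1 + 0.1 × 3.7/6.8 = 0.15 SD.

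**Step 4: true total effect of zero.** With a = 0.3–0.5 SD, the nominal 10% test rejects in 13–32% of trials. If MAAT-G helps mood more, 10–31% reject against MAAT-G and 0.3–2% for it. If supportive therapy does, these reverse.

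**Step 5: does the removal rule protect?** In simulation (6,000 trials per scenario, mood term dropped when p ≥ 0.10), the term stayed in 80–81% of trials at ρ = 0.3 and essentially all at ρ = 0.5. With the rule applied and a = 0.3–0.5 SD favouring MAAT-G, the estimate was 0.30–0.45, power 47–72% and null rejection 13–31%. The model without the term gave 78–80% power and about 10% null rejection in the same trials.

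**Step 6: does mood have to cause FACT-Cog?** No. In a large simulation where mood change and FACT-Cog shared only an unmeasured common cause (loadings 0.5), the adjusted estimate was 0.44 at a 0.3 SD difference and 0.39 at 0.5 SD. The model without the change term returned 0.52.

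**The case against.** **The base model is stated and powered.** Section 8.2 gives the arm plus pre-FACT-Cog model first and sizes the trial on it, so the adjustment could be read as a further step. But the text says the adjustment will be made, and does not say which fit is reported as primary.

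**The adjustment may apply only under imbalance.** The sentence can be read so that the imbalance condition also governs the change terms. That does not help: an arm difference in change is not a baseline imbalance, and if such a difference were the trigger, the adjustment would enter exactly when it does harm.

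**The mood difference may be small.** Supportive therapy "controls for non-specific psychotherapeutic factors of the clinician-subject relationship, such as empathy and support", so a difference near zero is plausible. At 0.1–0.2 SD the loss is modest, and at zero the adjustment helps. The lowest figures need 0.5 SD together with a correlation of 0.5. This stands as a limit on size.

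**The removal rule may drop the term more often.** Retention depends on inputs that the plan leaves open. With a 0.2 SD mood difference, a single term correlated 0.2 was kept in 52% of simulated trials. With two change terms intercorrelated 0.7 and joint correlation 0.3, at least one was kept in 49% when all non-significant terms were dropped together (mean estimate 0.49), and in 85% with stepwise backward removal. At correlation 0.5 retention was 91–100% either way. So the rule can soften the bias when the association is weak, but protects little when it is strong.

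**The null scenario is special.** If mood acts causally on FACT-Cog, a zero total effect with a mood difference needs a direct effect that cancels it exactly. If the association is not causal, no cancelling is needed. The figures in step 4 should be read with that qualification.

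**The evidence of an expected mood effect is thin, and this is a pilot.** The secondary-objective list is loosely drafted and the secondary hypothesis does not name mood. Cortisol is not among the measures in section 7.1 or the table in section 8.3.1. These points trim the periphery; a pilot still needs its primary estimate to answer its stated question.

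**Conclusion.** The concern holds: the primary model is wrong as written, because it adjusts for a post-randomisation variable while the stated target is MAAT-G's total effect on FACT-Cog. Confidence in the principle is high. The size is uncertain, since the between-arm mood difference and the mood–FACT-Cog correlation are both assumed. The effect runs from none (equal mood change) through a modest loss (0.1–0.2 SD) to a serious understatement or overstatement (0.3–0.5 SD), with the direction set by which arm helps mood more. Baseline GDS and GAD-7 adjustment and the stated sample size are not affected.

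**What to change.** In section 8.2, delete the words *and change* from the adjustment sentence. State that the primary estimate comes from post-FACT-Cog on arm and pre-FACT-Cog, with baseline GDS and GAD-7 included if wanted. Apply the same correction to the outcomes that inherit the strategy: objective cognition, IADL and, if it is still collected, cortisol. Add one sentence saying that any model with change in GDS or GAD-7 is an exploratory mediation analysis and does not drive the conclusion.

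The cost is two deleted words and a short addition to the SAP text, made before the outcome data are analysed. No data, visits or patients are added, and the analysis returns to the model that 35 per arm was calculated for.

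### The primary ANCOVA lets the trial's own data choose its covariates, so the model is not pre-specified and its standard error and p-value can be modestly too favourable

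*Combined protocol and SAP*

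**What the plan says.** The fixed part of the primary model (section 8.2, Analysis of the primary outcome) has post-FACT-Cog as outcome and will "include the arm as the main effect and pre-FACT-Cog as a covariate". Further terms depend on the data:

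- **Screen.** Under Quantitative Data Analysis, "Bivariate associations between treatment group and participant variables (demographics, cancer and treatment characteristics, baseline assessment of outcome measures) will be examined" for imbalance between arms. The primary-outcome paragraph then states "We will adjust for baseline covariates in case that imbalance between arms was detected".
- **Psychological terms.** The same sentence continues "and baseline and change in psychological measure (GDS and GAD-7".
- **Removal.** "All non-significant covariates will be removed from the model". Read literally, this does not exempt pre-FACT-Cog.
- **Interaction.** "We will evaluate the interaction between pre-FACT-cog and the arm", with no statement of what follows from the result.

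The plan does not list the candidates, say what counts as imbalance, or give the level or order of removal. It names no fixed-covariate analysis as the primary result. Secondary and exploratory outcomes follow the same strategy. The significance level is stated: the pilot "will use significance level=0.10 to avoid false negative results". Section 6.4 stratifies randomisation by stage (I-III versus IV), but stage is not named as a model term.

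**The concern.** Under randomisation, a baseline difference between arms arises by chance. A screen for imbalance therefore selects covariates by luck rather than by how well they predict FACT-Cog. Removing terms according to their p-values in the same outcome model that tests the arm is a second selection on the same data. The final model's standard error treats the surviving covariates as if they had been chosen beforehand.

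The estimate at stake is the preliminary efficacy result the trial exists to produce. If the analysis cannot be written down beforehand, the stated 0.10 level cannot be verified. The 80% power in section 8.2 describes only the arm plus pre-FACT-Cog model, not the procedure that would be run.

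**Working it through.** **1. The plan's own figure.** Inputs from section 8.2: 35 evaluable per arm, d = 0.52, pre-post correlation 0.5, level 0.10 (two-sided, by the default in 8.1.2).

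- Residual SD = √(1 − 0.5²) = 0.866.
- SE = 0.866 × √(2/35) = 0.207, and 0.52/0.207 = 2.51.
- Normal approximation: Φ(2.51 − 1.645) = 80.7%. Noncentral t on 67 df: 80.0%.
- Enrolment: 70/0.85 = 82.4, so 83, against 85 planned.

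The stated power is right for arm plus pre-FACT-Cog.

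**2. How often chance triggers the screen.** The plan gives categories, not a count. Section 7.1 names seven demographics, unspecified cancer and treatment variables, and nine baseline instruments (eleven measures if the three CANTAB tests are counted separately). Some of these are already in the model or enter through the GDS/GAD-7 clause. Twenty candidates is therefore an assumption, as is a 0.10 screen.

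- Expected number flagged: 20 × 0.10 = 2.0.
- At least one flagged, if independent: 1 − 0.9²⁰ = 88%. With mutual correlation 0.2, by simulation: 84%.
- With a 0.05 screen and the same correlation: about 59%.

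**3. Twenty correlated candidates.** Simulated trials with 35 per arm: screen at 0.10, baseline GDS and GAD-7 always entered, backward removal at 0.10, arm tested at 0.10. Baseline GDS and GAD-7 together explain 0-20% of post-score variance beyond pre-FACT-Cog. The change terms were not simulated.

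- False-positive rate over 7,000 null trials per scenario: 10.8-11.5%, against 9.6-10.3% for fixed pre-FACT-Cog, baseline GDS and baseline GAD-7. The Monte Carlo SE is √(0.1 × 0.9/7,000) = 0.4 points. Repeat runs gave 11.2-11.7% under selection.
- Reported SE about 3-5% too small (for example 0.181 against a true 0.189).
- About 190-200 different final models arose over 6,000 null trials. The selected and fixed models disagreed on significance in 3-4% of trials, rising to 8-12% when the other candidates were also prognostic.

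**4. Other assumptions.** 5, 10 or 20 independent candidates explaining 0, 20 or 40% of residual variance; null trials at nominal 0.10; 15,000 trials per scenario for the first two rows, 8,000 for the next two and 3,000 for the last.

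| Procedure | False-positive rate | Reported SE / true SE |
|---|---|---|
| Screen, then removal | 0.084-0.112 | 0.97-1.05 |
| Same, plus four GDS/GAD-7 terms unrelated to arm and outcome, also pruned | 0.089-0.114 | 0.95-1.04 |
| Imbalance screen alone | 0.077-0.101 | up to 8% too large |
| Removal alone, from the full list | 0.108-0.182 | up to 18% too small |
| Success if any of six threshold readings gives p < 0.10 | 0.116-0.149 | not computed |

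Rows three and four locate the source: optimism comes from outcome-based removal, not from the screen. Row four is not the plan's procedure, because only flagged variables and the GDS/GAD-7 terms enter. The last row uses screens at 0.05, 0.10 or 0.20 and removal at 0.05 or 0.10. It shows what leaving the thresholds open can cost.

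**5. The change terms.** Change in GDS and GAD-7 is measured after randomisation and may be affected by the arm. As an illustration, assume the arm lowers each by 0.3-0.5 SD, each has an outcome slope of 0.2-0.3 per SD in the direction of worse cognition, and the true total effect is 0.52. The mean simulated estimate falls to between 0.42 and 0.22, and power to between 66% and 32%. Simple subtraction is close: 0.52 − 2 × 0.3 × 0.2 = 0.40, and 0.52 − 2 × 0.5 × 0.3 = 0.22.

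**The case against.** A reader might infer that the test necessarily exceeds its 0.10 level, that the intervals are always too narrow, or that the plan tilts the result towards MAAT-G. The documents do not support any of these. The number and strength of the candidates are not stated. With few, strongly prognostic candidates the false-positive rate falls to 8.4% and the reported SE is too large. The screen alone is neutral or conservative. The change terms, if the arm improves mood or anxiety, pull the estimate against MAAT-G.

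Nor does the plan say that some 20 variables are tested at 0.10. The 0.10 level is stated next to the screen but is not attached to imbalance detection, and the general default is 5%.

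It can also be said that this is a pilot with a deliberately liberal level, and that an excess of about one point matters little. That stands as a limit on the size of the problem. It does not supply the missing rule: nothing else in the documents fixes the primary model, and a liberal level still has to be one the analysis can be shown to meet.

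A last argument is that selection might gain power. It does not do so materially: in 2,500 trials per scenario the fixed set gave 83.1% against 82.4%, and 88.0% against 87.4%. With a Monte Carlo SE of about 0.65-0.75 points per figure, these are equal for practical purposes.

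**Conclusion.** The concern holds as one of pre-specification. The trial's data choose the covariates, the thresholds are open, and the final standard error and p-value are not guaranteed valid.

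They can be modestly too favourable: about 11-11.5% false positives against 10%, with an SE about 3-5% too small. That rests on about 20 candidates correlated 0.2, screening and removal at 0.10, and no change terms in the simulation. Over the independent-candidate scenarios the range is about 8.4-11.4%, so the direction is not settled. Choosing among readings of the thresholds after seeing the results would cost more, at 11.6-14.9%.

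Confidence is high that the model is data-driven and low on the direction of the error in this trial. The plan should be changed, but this is not a fatal flaw. The post-randomisation change terms in the same sentence could have the larger effect and need to be dealt with by name.

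**What to change.** Delete the imbalance-triggered adjustment and the removal rule as drivers of the primary model. State the model in full: post-FACT-Cog on arm, pre-FACT-Cog, stage (the stratification factor), baseline GDS and baseline GAD-7, all kept whatever their p-values. State that change in GDS and GAD-7 is not in the primary model because it is measured after randomisation and may be affected by the arm. State also that the evaluation of the interaction does not alter this model.

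Use the same rule for each secondary outcome, with that outcome's own baseline value. Present baseline characteristics by arm descriptively. Label any further adjustment, including for a variable that looks imbalanced, as a sensitivity analysis.

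With a fixed baseline set the simulated level was 0.095-0.103, and the sample size need not change. The cost is wording and three degrees of freedom (stage, GDS, GAD-7), about one point of power if the added covariates prove not to be prognostic. Arm plus pre-FACT-Cog and stage would also be a valid fixed set; what matters is that the list is settled before the data are seen.
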